# 13.2 Sample Size and Power Determination

The sample size and power are calculated based on Simon's two-stage minimax design, which minimizes the expected maximum sample size under the alternative hypothesis. The previous 2 years at VCU have seen an ~15% NRM rate in MRD patients and an ~40% NRM rate in MUD patients. Given that MRDs comprise ~25% of total transplantations and MUDs comprise ~75%, we then assume an overall 35% NRM rate. The null hypothesis that the NRM rate is 35% will be tested against a one-sided alternative. In order to achieve 80% power (with 5% significance) to declare an NRM of 20% significantly smaller than the

hypothesized null NRM of 35%, we will accrue 31 patients in stage 1 and an additional 24 patients in stage 2 (provided the trial is not stopped early for futility). At the end of stage 1, if there are 11 or more NRMs in the 31 stage 1 patients, the study will be stopped for futility. Otherwise, 24 additional patients will be accrued for a total of 55. The null hypothesis will not be rejected if 14 or more NRMs are observed in the total 55 patients. We anticipate a 32% screen failure rate, leading to a recruitment target of 81 subjects (VCU sees ~5 eligible MRD/MUD patients per month). The number of MUD patients will be limited to 80%.

The population evaluable for the primary endpoint includes all patients who receive at least one dose of IV vitamin C and who have a known survival status at one year. Patients who are enrolled to the study but do not receive any IV vitamin C or who are lost to follow up at one year will be replaced.

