## 13.1.4 Statistical Analysis

The primary and secondary outcomes will be compared between the study cohort and a historical cohort matched for age, donor type, and diagnosis. The NRM rate will be compared to the historical 35% rate (see Section 13.2 below) using a onesided exact binomial test. Time-to-event outcomes (time to engraftment, acute and chronic GVHD, and overall and relapse-free survival) will be graphically represented with a Kaplan-Meier step-function and will be assessed for associations with serum vitamin C levels and patient demographic measurements using a Cox Proportional Hazards model. Associations between blood levels of vitamin C and other exploratory endpoints will be estimated using Spearman rank correlation coefficients.

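### The 35% null matches the plan's own donor-specific NRM rates only at the 80% MUD cap; at the planned 75% the one-sided error is 7.1%, and no lower limit on the MUD share bounds it

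*Combined protocol and SAP*

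**What the plan says.** Section 13.2 gives the local history: "The previous 2 years at VCU have seen an ~15% NRM rate in MRD patients and an ~40% NRM rate in MUD patients". It weights these at roughly 25% MRD and 75% MUD, takes the overall rate as 35%, and states: "The null hypothesis that the NRM rate is 35% will be tested against a one-sided alternative". The design is a Simon minimax with 31 patients in stage 1 and 24 in stage 2. Accrual stops for futility "if there are 11 or more NRMs in the 31 stage 1 patients, the study will be stopped for futility", and the null is kept if 14 or more of the 55 patients have NRM, so 13 or fewer is a positive result. On donor mix the section says "The number of MUD patients will be limited to 80" percent. It sets no minimum MUD share and no maximum MRD share, and Sections 3.1, 4.1 and 4.2 add none.

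Section 13.1.4 makes the primary test a one-sided exact binomial: "The NRM rate will be compared to the historical 35% rate". The test is neither stratified nor re-weighted by donor type. The same paragraph also says: "The primary and secondary outcomes will be compared between the study cohort and a historical cohort matched for age, donor type, and diagnosis". It gives no test, matching method or decision rule for that second comparison.

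**The concern.** By the plan's own account, NRM without the drug differs by about 25 percentage points between donor types, so the rate expected with no effect depends on who is enrolled. The benchmark does not follow the enrolled mix. The cap prevents a mix that would push the expected rate above 35% at the stated rates. Nothing limits a mix that pulls it below. A cohort with fewer MUD patients would tend to show lower NRM than 35% without any contribution from vitamin C, and the decision rule could not tell the two apart. The primary objective is the effect of vitamin C on one-year NRM, so this bears directly on what a positive result can support.

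**Working it through.** **Inputs.** All from Section 13.2: NRM 15% (MRD) and 40% (MUD), both approximate; null 35%; alternative 20%; 31 + 24 = 55 patients; continue if at most 10 of 31; positive if at most 13 of 55; MUD share s at most 0.80; planned s = 0.75.

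**Formula.** Chance of a positive result at true NRM p:

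P(p) = sum over x = 0 to 10 of Bin(x; 31, p) x Pr[Bin(24, p) <= 13 - x].

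**The plan's own figures.** P(0.35) = 0.0484 and P(0.20) = 0.8006, which agree with the stated 5% and 80%. A search over total sizes from 50 to 56 finds no qualifying design below 55, and 10/31 with 13/55 has the smallest expected size under the null at 55. The design arithmetic is correct.

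**No-effect NRM by donor mix.** p0(s) = 0.15(1 - s) + 0.40s = 0.15 + 0.25s. The last column holds the donor counts fixed in each stage instead of giving every patient the average risk.

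| MUD share | No-effect NRM | Error of the 13/55 rule | Error, fixed donor counts |
|---|---|---|---|
| 80% (cap) | 35.0% | 4.8% | 4.5% |
| 75% (planned) | 33.75% | 7.1% | 6.8% |
| 70% | 32.5% | 10.1% | 10.0% |
| 60% | 30.0% | 18.8% | 17.9% |
| 50% | 27.5% | 31.6% | 29.4% |

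On the average-risk calculation, 5% is exceeded once the MUD share falls below about 79.5%.

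**What belongs to the 75% row.** 0.25 x 15% + 0.75 x 40% = 33.75%, not 35%. The rise from 4.8% to 7.1% comes from that difference and needs no drift in mix. With a null of 33.75% and the matching limit of 12/55, the error would be 3.8% at 75% MUD, 5.7% at 70% and 11.7% at 60%. Correcting the arithmetic alone therefore deals with the planned mix and nearly deals with 70%, but not with a larger shift.

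**How likely the lower rows are.** If each patient is MUD with probability 0.75, Pr(at most 33 of 55, i.e. 60%) = 0.010 and Pr(at most 27 of 55) is about 0.00003.

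**Sensitivity to the donor rates.** Section 1.1 gives 10-20% for MRD and 20-40% for MUD. At the 80% cap the corners are:
- MRD 20%, MUD 40%: 0.2 x 20 + 0.8 x 40 = 36%
- MRD 10%, MUD 40%: 34%
- MRD 20%, MUD 20%: 20%
- MRD 10%, MUD 20%: 18%

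One corner lies above the null and the others below it.

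**Limits that hold 5% for a mix-weighted null, same stage 1 rule.**

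| MUD share | Limit in 55 | Error at that mix | Power at 20% NRM |
|---|---|---|---|
| 80% | 13 | 4.8% | 80% |
| 75% | 12 | 3.8% | 70% |
| 70% | 11 | 3.0% | 58% |
| 60% | 10 | 3.4% | 45% |
| 50% | 9 | 4.0% | 32% |

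**The case against.** A fixed historical null is a common choice in single-arm phase 2 trials, and the plan already names a comparison matched for donor type. At the only mix the documents support, the error is 7.1%, and that excess comes from the 25/75 arithmetic rather than from drift. All of this stands, and it limits the size of the point. What it leaves open is that the matched comparison has no method and no bearing on the 13/55 decision, so the plan does not say what follows if the two disagree.

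A reader might infer four stronger things that the documents do not support:
- That every permitted mix has a no-effect NRM at or below 35%. This holds only at the point rates. MRD 20% with MUD 40% gives 36% at the cap. Sections 3.1 and 4.1 also admit mismatched donors, for whom no NRM rate is given; a higher rate there could take a permitted mix above 35%.
- That chance variation in donor mix adds further error. Under 75% referral a share of 70% or less occurs in about 19% of 55-patient cohorts, but the 7.1% already averages over random mix, so this is not an extra risk.
- That errors of 19% or 32% are to be expected. They need a systematic change in referral or enrolment, which the protocol permits but nowhere describes.
- That the cap was set to favour the trial. Section 13.2 gives no reason for it.

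**Conclusion.** The point holds as a moderate weakness in the decision rule. At the rates in Section 13.2, the nominal 5% is met only at, or within about half a percentage point of, the 80% MUD cap. The error is 7.1% at the planned mix and about 10% at 70% MUD, and it keeps rising below that with no floor on the MUD share. These figures treat the approximate 15% and 40% as known and count all unrelated donors as MUD. The direction could reverse near the cap if MRD risk is closer to 20% or if mismatched donors do worse. The Simon calculation itself is sound; the gap is that a fixed benchmark is applied to a donor mix that can move, with nothing in the analysis that ties the conclusion to the mix actually enrolled.

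**What to change.** Keep the cap, and keep the 35% Simon rule as the formal design. In Section 13.1.4:

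1. Pre-specify, beside the 35% test, an exact test of one-year NRM against p0 = 0.15 x (MRD share) + 0.40 x (MUD share) of the evaluable patients. Use the same stage 1 rule and fix the limits in advance: 13/55 at 80% MUD, 12 at 75%, 11 at 70%, 10 at 60% and 9 at 50%. For shares in between, use the largest count that keeps the two-stage error at or below 5%.
2. Show how that benchmark changes over the Section 1.1 ranges, and say how mismatched donors are classed.
3. Report NRM by donor type.
4. State that a result passing 35% but not the mix-weighted benchmark will be reported as not distinguishable from donor mix.

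The cost is SAP wording and one further exact test on data already collected; enrolment and treatment do not change. The drawback is power. Against 20% NRM the weighted test has about 70% at the planned mix (12/55), 58% at 11/55 and 45% at 10/55, compared with 80% for the stated rule. Whether to make it a joint requirement for success is therefore the sponsor's choice and is not part of this change.

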# 6 TREATMENT PLAN

## 6.1 Study Treatment

6.1.1 Safety Lead-In Cohort

For the initial safety lead-in cohort of 14 patients, vitamin C deficiency will be confirmed by a standard clinical pathology laboratory blood test before the first dose of parenteral vitamin C (see Sections 12 and 13.3). Safety lead-in patients with confirmed vitamin C levels of 0.5 mg/dL or less (20) may proceed on study treatment.

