6.5.2 Non-Relapse Mortality

Follow-up for NRM will continue for one year following transplantation per standard post-transplant procedures or until relapse or death, whichever occurs first.

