# 7 DOSING DELAYS/DOSE MODIFICATIONS

## 7.1 Vitamin C

During days 1-14, IV vitamin C will be held in patients who develop a serum creatinine of >2.0 mg/dL and resumed once serum creatinine is  $\leq$  2.0 mg/dL. Missed doses will not be made up.

During days 15-180, if a patient has a serum creatinine level of > 2.0 mg/dL definitely, probably, or possibly related to vitamin C (Section 8.1.8), the patient will be instructed not to take their oral vitamin C until the serum creatinine level is  $\leq$  2.0 mg/dL. Missed doses will not be made up.

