# **12 STUDY CALENDAR**

Required assessments, tests, examinations, administration of the vitamin C regimen, and collection of blood samples for correlative studies are outlined on Table 4 and Table 5.

Tests, Exams, Procedures, and Other Requirements A	Timeline				
Informed Consent	Prior to initiation of SCT preparative treatments				
Demographics					
Medical History					
Physical Exam					
Performance Status					
Weight & Height					
HLA Typing B					
CBC, Differential, Platelets	Timing prior to study enrollment should be				
Blood Chemistries C	consistent with the usual MCC-VCUHS CIT				
Creatinine Clearance	Program practices to screen patients for				
Infections Disease Titers D	SC1.				
G6PDH Deficiency Testing					
Cardiac Assessment E					
Chest X-Ray or Chest CT					
Disease Staging F					
Baseline Symptoms	-				
Urinalysis					
Serum Pregnancy Test	As applicable, within 30 days prior to initiation of the SCT preparatory regimen				
Vitamin C Test G	Within 2 to 5 days prior to transplant day 0				
Correlative Blood Sample Collection	After study registration but before initiation of the SCT preparatory regimen				

 
Table 4 Footnotes: 
 
A. In addition to the assessments/tests listed, other tests and exams may be performed per standard guidelines for the MCC-VCUHS CIT program and per investigator discretion.
 
B. Donor and recipient
 
C. Blood chemistries include serum creatinine, total bilirubin, alkaline phosphatase, AST, ALT, and additional tests per investigator discretion.
 
D. Infectious disease markers per standard VCU CIT program practices.
 
E. Cardiac assessments include ECG and left ventricular ejection fraction or shortening fraction by echocardiogram or MUGA.
 
F. Relevant and disease-specific staging according to the MCC-VCUHS CIT Program usual practice.
 
G. For safety lead-in cohort patients only
 
 
 
					

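### Section 13.2 makes known one-year survival status a condition of the primary analysis, so a patient who relapsed and was then lost is replaced although the outcome (no NRM) is known; no sensitivity analysis covers all transplanted patients

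*Combined protocol and SAP*

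**What the plan says.** Section 13.2 sets two conditions for the primary endpoint population: at least one IV dose, and survival status known at one year. Enrolled patients who "do not receive any IV vitamin C or who are lost to follow up at one year will be replaced".

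Four other places matter.

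- **Endpoint.** Section 1.1 describes NRM as death from transplant complications rather than relapse. Section 6.5.2 continues NRM follow-up for one year "per standard post-transplant procedures or until relapse or death, whichever occurs first".
- **Dosing.** Section 6.1.2 starts IV vitamin C on Day +1. Under Section 7.1, during Days 1-14, "IV vitamin C will be held in patients who develop a serum creatinine of >2.0 mg/dL".
- **Analysis.** Section 13.1.4 states: "The NRM rate will be compared to the historical 35% rate", by a one-sided exact binomial test. It also plans a comparison with a matched historical cohort. No NRM analysis is described for any population other than that of Section 13.2.
- **Follow-up and records.** Section 10.2 follows all study patients, including those off treatment, for survival every 3 months. Section 5.2 records the reason and date of withdrawal.

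**The concern.** The evaluability rule asks whether the patient is known to be alive or dead at one year. The endpoint asks something else: whether the patient died without relapse within the year. The two come apart for a dosed patient who relapses at, say, month 5 and is lost at month 8. Under Section 6.5.2 that patient's NRM question closed at relapse with the answer no. Under Section 13.2 the patient is discarded and replaced. Every such replacement removes a known non-event, raises observed NRM and works against the drug. The design has almost no power to spare.

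A second group is removed after transplant: patients never dosed because of death or withdrawal before the first dose, or because creatinine kept the drug on hold throughout Days 1-14. The 35% benchmark is described only through shares of transplantations and NRM in related- and unrelated-donor patients, with no condition on a later treatment or on follow-up. In a single-arm comparison with a fixed rate, a reader would want to see that this removal did not drive the result, and no planned analysis shows it.

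**Working it through.** **Inputs.** From Section 13.2: null NRM 35%, target 20%, 31 patients in stage 1 (stop at 11 or more NRMs), 55 in total (positive at 13 or fewer), 5% one-sided significance, 80% power. The documents give no replacement rate, so the shares below are assumptions.

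**1. The plan's own figures.** With X1 ~ Bin(31, p) and X2 ~ Bin(24, p), P(positive) = sum over x1 = 0 to 10 of P(X1 = x1) × P(X2 ≤ 13 − x1).

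- p = 0.35: 0.0484
- p = 0.20: 0.8006

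The stated design reproduces.

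**2. Effect of removal.** If a share f with NRM rate q is removed from a population whose NRM is π, the evaluable patients have NRM = (π − f·q)/(1 − f). Put this rate into step 1.

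**3. Relapsed, then lost (q = 0 by definition).**

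| f | NRM if π = 0.20 | Power | NRM if π = 0.35 | False-positive rate |
|---|---|---|---|---|
| 0 | 0.2000 | 80.1% | 0.3500 | 4.84% |
| 1% | 0.2020 | 79.0% | 0.3535 | 4.3% |
| 2% | 0.2041 | 77.8% | 0.3571 | 3.9% |

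These shares mean 55f/(1 − f) = 0.6 to 1.1 such patients per 55 evaluable.

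**4. Transplanted, never dosed (inert drug, π = 0.35).** Their NRM is unknown, so q is varied.

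| q | False-positive rate, f = 0.5% | f = 1% |
|---|---|---|
| 80% | 5.2% | 5.6% |
| 60% | 5.0% | 5.2% |
| 45% | 4.9% | 5.0% |
| 20% | 4.7% | 4.6% |

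The rate moves up or down depending on whether these patients do worse or better than average.

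**5. When one patient could matter.** Single-stage exact p-values against 35%:

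- 13/55: 0.049. Adding one never-dosed NRM death gives 14/56: 0.074.
- 12/55: 0.025. The same addition gives 13/56: 0.041, still below 5%.

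Only a result of exactly 13/55 is overturned by one added death. Reaching that result has probability 0.023 at NRM 35% and 0.099 at 20%. The chance of at least one never-dosed NRM death among 55 is 1 − (1 − f·q)^55, or 12% (f = 0.5%, q = 45%) to 36% (f = 1%, q = 80%). Multiplying, about 0.3-0.8% of trials would be affected if the drug is inert, and 1.2-3.5% if NRM is 20%.

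**The case against.** The rule was fixed in advance, and a treated-and-followed population with replacement is an ordinary phase 2 choice. Loss should be rare, since Section 10.2 requires survival contact every 3 months. A single dose makes a patient evaluable on the dosing condition, so few transplanted patients will go undosed. Much of the raw information will exist: withdrawal reasons, serious adverse events including deaths, and survival. The Kaplan-Meier curve for overall survival can carry lost patients as censored.

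All of this stands, and it is why the point is minor. None of it supplies an NRM analysis that includes the replaced patients, and none of it mends the mismatch between survival status and NRM status.

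Three stronger readings are tempting and are not supported.

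- **That replacement inflates the false-positive rate.** This needs many replaced patients who are mostly NRM deaths. The documents give neither a number nor an outcome. At plausible shares the rate stays near 5%, and the relapsed-then-lost group pushes it below the designed 4.84%.
- **That every enrolled patient belongs in the comparison.** A patient never transplanted cannot have NRM after transplant and lies outside the transplant-based 35%. Leaving that patient out matches the benchmark. Nor is a mismatch with the 35% shown for the never-dosed, because its derivation is not described in enough detail.
- **That the lead-in vitamin C cutoff is a further source of bias.** Section 6.1.1 lets "Safety lead-in patients with confirmed vitamin C levels of 0.5 mg/dL or less" proceed, and the test sits in the screening table (Table 4). How to classify those above the cutoff is a matter of screening and recruitment. It does not show that NRM is distorted.

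**Conclusion.** The concern holds as a minor one. The firm part is definitional and needs no assumed rate: following Section 13.2 literally discards patients whose primary outcome is already known to be no NRM. The direction is against the drug. The size depends on an assumed 1-2% frequency and is a loss of 1 to 2 points of power, from 80.1% to 79.0-77.8%.

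The softer part is that transplanted but never-dosed patients leave the analysis after enrolment and no sensitivity analysis brings them back. At an assumed 0.5-1%, with their NRM anywhere from 20% to 80%, the false-positive rate lies between 4.6% and 5.6%. The direction is not established. Neither part undermines the sample size, the stopping rule or the 13/55 criterion.

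**What to change.** - **Section 13.2.** Keep the one-dose condition, and replace known survival status with known NRM status at one year: alive at one year, relapse documented within the year, or death within the year with its cause known. State that a patient who relapses and is then lost counts as no NRM and is not replaced. Keep 31 + 24 = 55 and the 13/55 rule.
- **Section 13.1.4.** Add a required sensitivity analysis of NRM against 35% in all transplanted enrolled patients, including the never-dosed. Count patients lost without documented relapse once as NRM and once as no NRM, and treat any death of undetermined cause the same way.

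The cost is a few lines of text, plus relapse status and cause of death for a few extra patients. At the assumed 0.5-1%, 55f/(1 − f) gives 0.3 to 0.6 never-dosed patients per 55. Survival follow-up is already planned, though outcomes may be unobtainable where consent is withdrawn. The sensitivity estimate may be slightly less favourable than the primary one.

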# 10.2 Length of Relapse-Free/GVHD-Free Survival and Survival

All study patients including those removed from the treatment protocol will be followed for survival every 3 months.

- Length of relapse-free/GVHD-free survival is measured from transplant to relapse, GHVD diagnosis, death, or time of last contact, censoring for patients alive and relapse-free/GVHD-free at the time of last contact.
- Length of survival is measured from transplant to death or time of last contact, censoring for patients alive at time of last contact.

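### The rule replacing lost patients makes evaluability for one-year NRM depend on outcome, and discards relapsed patients whose NRM status is already settled

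*Combined protocol and SAP*

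**What the plan says.** Section 13.2 defines the primary population as patients given at least one IV dose "who have a known survival status at one year". Patients never dosed are replaced, and so are those "who are lost to follow up at one year will be replaced".

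Section 1.1 defines NRM as death from transplant complications, excluding relapse. Section 6.5.2 follows patients for NRM for one year "or until relapse or death, whichever occurs first".

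Section 10.2 adds: "All study patients including those removed from the treatment protocol will be followed for survival", at three-month intervals.

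The primary analysis (Section 13.1.4) compares the NRM rate with 35% "using a onesided exact binomial test". On the design, Section 13.2 says: "The sample size and power are calculated based on Simon's two-stage minimax design". It enrols 31 + 24 = 55 patients, stops at 11 or more NRM events in the first 31, and does not reject at 14 or more in 55. The recruitment target of 81 allows for screen failure only. The plan gives no loss-to-follow-up rate and no sensitivity analysis for lost patients.

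**The concern.** Two features of the rule matter.

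- **Selection on outcome.** A death that becomes known makes a patient evaluable. A patient who loses contact while alive is removed after dosing, and a new patient takes the place. Replacement restores the count of 55 but does not undo the selection.
- **Two completion criteria for one endpoint.** Section 6.5.2 closes NRM follow-up at relapse. Section 13.2 requires survival status at one year. A patient who relapses at month 4 and is lost at month 8 is complete under the first and excluded under the second. Everyone excluded this way is a non-event.

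The tested proportion may therefore differ from the NRM rate among dosed patients. The decision turns on a single event (13 or 14 of 55), so the status of one or two patients can settle it.

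**Working it through.** **Inputs.** From Sections 13.1.4 and 13.2: null NRM 35%, alternative 20%, one-sided 5%, continue at 10 or fewer of 31, reject at 13 or fewer of 55. The loss rate is not given, so 2%, 5% and 10% are assumptions.

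**1. The plan's own figure.** The probability of rejecting at NRM rate p is

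R(p) = sum over x = 0 to 10 of P(Bin(31,p) = x) × P(Bin(24,p) ≤ 13 − x).

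R(0.20) = 80.06% and R(0.35) = 4.84%. The stated 80% and 5% reproduce, with almost no slack in power. The chance of a stage 1 stop, P(Bin(31,p) ≥ 11), is 3.3% at 20% NRM.

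**2. Loss unrelated to prognosis.** Assume constant hazards and no relapse, and let c be the chance of being lost by one year if death does not come first. With true NRM of 20%:

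- death hazard = −ln(0.80) = 0.2231; loss hazard = −ln(1 − c)
- known alive at one year: A = 0.80 × (1 − c)
- deaths seen: D = 0.2231 / (0.2231 + loss hazard) × (1 − A)
- evaluable NRM = D / (D + A)

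For c = 10%: loss hazard = 0.1054, A = 0.72, D = 0.2231/0.3285 × 0.28 = 0.1902. Evaluable NRM = 0.1902/0.9102 = 20.9%. Because some patients die first, the share actually excluded is 1 − 0.9102 = 9.0%.

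**3. No lost patient has NRM.** If a share L of all dosed patients is lost, evaluable NRM = 0.20/(1 − L). Type I error uses 0.35/(1 − L).

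| Loss | Step 2: evaluable NRM | Power | Type I error | Step 3: evaluable NRM | Power | Type I error |
|---|---|---|---|---|---|---|
| 0 | 20.0% | 80.06% | 4.84% | 20.0% | 80.06% | 4.84% |
| 2% | 20.2% | 79.2% | 4.5% | 20.4% | 77.8% | 3.8% |
| 5% | 20.4% | 77.7% | 4.0% | 21.1% | 74.1% | 2.6% |
| 10% | 20.9% | 75.0% | 3.2% | 22.2% | 66.7% | 1.2% |

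At 10% loss, the chance of a stage 1 stop at a true NRM of 20% rises from 3.3% to 4.4% (step 2) or 6.5% (step 3).

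**4. The relapse part.** Extend step 2 with an assumed 25% relapse by one year, no deaths after relapse, and 10% loss. Deaths seen are 0.1908, and patients alive, relapse-free and still followed are 0.55 × 0.90 = 0.495.

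- Section 13.2 rule: relapsed patients count only if still followed at one year, 0.25 × 0.90 = 0.225. Evaluable NRM = 0.1908/(0.1908 + 0.225 + 0.495) = 20.9%; power 74.7%.
- Relapse settles status: every relapse seen before loss counts, 0.2385. Evaluable NRM = 0.1908/(0.1908 + 0.2385 + 0.495) = 20.6%; power 76.5%.

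**5. The lost do worse than the cohort.** Let 10% be lost and a share f of them have unseen NRM. Evaluable NRM is (0.20 − 0.10f)/0.90 at the alternative and (0.35 − 0.10f)/0.90 at the null.

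- f = 20%: 20.0% at the alternative; power unchanged at 80.06%.
- f = 40%: 17.8% at the alternative, power 90.0%; 34.4% at the null, type I error 5.75%.

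**The case against.** A reader might infer that one-year NRM is biased upward and that the stated 80% power is not delivered. The documents do not support either as a certainty. With no loss the design has 80.06% power, and no loss rate is given. Deaths stay evaluable only if they become known: a patient can lose contact and then die of transplant complications. As step 5 shows, the direction depends on who is lost. The step 3 figures are an extreme, because they assume that none of the lost has NRM.

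The plan also limits loss. Evaluability needs only vital status, not a completed visit. Section 10.2 continues survival contact for patients off treatment, Section 6.5.3 runs it to two years, and Table 5 allows year 2 follow-up by telephone or through the referring physician. A later contact can establish that a patient who missed day 365 was alive at one year. Relapse followed by unknown vital status may therefore be rare.

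Under non-informative loss, type I error falls, so that case creates no false claim of benefit.

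All of this stands, and it limits the size of the problem. It does not change the written rule, and it does not explain why a patient with settled NRM status should be discarded.

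**Conclusion.** The concern holds as a defect in the evaluability rule, with a conditional effect. That the rule selects on outcome, and that it conflicts with Section 6.5.2 over relapsed patients, follows from the text. The conflict rests on reading Sections 1.1 and 6.5.2 together as making relapse a non-event for NRM; it needs no assumption about who is lost.

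The numerical effect does rest on assumptions. If loss is unrelated to prognosis, NRM is biased upward and power falls from 80.06% to about 79%, 78% and 75% at 2%, 5% and 10% loss. If no lost patient has NRM, it falls further, to 66.7% at 10%. If NRM among the lost is well above the cohort rate, the bias turns in favour of vitamin C and type I error can pass 5%. The sample-size calculation itself is correct. The change is worth making because it is cheap and the margin is a single event.

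**What to change.** In Section 13.2:

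- Define evaluable as dosed with known NRM status at one year. Relapse before loss counts as a non-event, and that patient is not replaced.
- Keep the exact binomial test and the 10/31 and 13/55 limits as the primary rule.
- For dosed patients lost alive and relapse-free, report best-case (no NRM) and worst-case (NRM) counts against 13/55, and against 10/31 at stage 1. Taking the first 31 and first 55 dosed patients in order of enrolment keeps those denominators valid.
- Add a one-year cumulative incidence estimate, with relapse as the competing event, as supportive only.

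A cumulative incidence limit should not replace the primary test without a new design calculation. In a simulation of 40,000 trials with independent loss and no relapse, requiring a plain Greenwood upper limit below 35% gave type I error of about 6% and 7% at 5% and 10% loss. A log-log limit gave power of about 75% and 74%, no better than the present rule.

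The cost is a short edit and a little more analysis, with no new patients or data. The edit does not remove all bias: in step 4 power recovers to 76.5%, not 80%. The best-case and worst-case counts are there to show what remains.
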